8.7.1. Analyses of Liver Function Tests

A summary of Liver Monitoring/Stopping Event Reporting will be provided. A Liver event profile which includes medical conditions data for subjects with liver stopping events, substance use data for subjects with liver stopping events, liver biopsy results for subjects and recorded outcomes of liver imaging assessments for subjects will be listed.

Summaries of hepatobiliary laboratory abnormalities including possible Hy’s law cases will be provided. A summary of liver restart/re-challenge timings will be provided.

Plots of maximum total bilirubin versus maximum ALT, maximum ALT versus baseline ALT, maximum AST versus maximum LDH, maximum AST versus maximum Creatinine Kinase, and maximum LDH versus maximum Creatinine Kinase will be generated. A plot of maximum albumin/creatinine ratio (greater than 2000 mg/g) versus

concomitant serum concomitant will be provided. Serum creatinine will be considered as concomitant only if the start date is within ± 7 days of the ongoing lab event.

8.8. Other Safety Analyses

The analyses of non-laboratory safety test results including ECGs and vital signs will be based on GSK Core Data Standards, unless otherwise specified. LVEF and Performance status will be summarized and listed based on GSK Oncology Data Standard. The details of the planned displays are presented in [Appendix 11: List of Data Displays](#).

8.8.1. Performance Status

ECOG performance status will be summarized at baseline and each post-baseline scheduled visit. Summaries will use frequency and percentage of subjects at each planned assessment time. A summary of change from baseline by scheduled visits will be performed, as well as the worst case post-baseline and the best case post-baseline changes during the study (improved, no change, deteriorated).

8.8.2. ECG

A summary of the number and percentage of subjects who had normal and abnormal (clinically significant and not clinically significant) ECG findings will be displayed by scheduled visits as well as for the worst case post-baseline.

The QTc values based on Fridericia formula will be rounded to the integer and the values will be categorized into the following ranges: Grade 0 [CCI](#) [REDACTED], Grade 1 [CCI](#) [REDACTED], Grade 2 [CCI](#) [REDACTED], and Grade 3 [CCI](#) [REDACTED]. Summaries of grade increase will be provided. These summaries will display the number and percentage of subjects with any grade increase.

The changes in QTc values will be categorized into the clinical concern ranges which are specific to changes in QTc: 31-60 and >60 msec. A summary of change in QTc value will display the number and percentage of subjects with a change within each range in the worst case post-baseline only. Subjects with missing baseline values will be excluded from this summary.

A listing of QTc values of potential clinical importance will be provided.

The summaries and listing of QTc will use the collected values based on Fridericia formula.

A Figure plotting the baseline QTc and the worst-case post-baseline values will be produced. The Figure will have reference lines at 480 and 500 msec for both the ordinate and the abscissa axes. There will be diagonal reference lines at equality (i.e. a 45 degree line), at equality plus 30 msec, and at equality plus 60 msec.

8.8.3. LVEF

Absolute change from baseline in LVEF will be summarized in the worst case post-baseline only. Only the post-baseline assessments that used the same method (ECHO or MUGA) as the baseline assessments will be used to derive the change from baseline. The change from baseline will be categorized as follows:

- No change or any increase
- Any decrease
 - >0-<10 decrease
 - 10-19 decrease
 - >=20 decrease
 - >=10 decrease and >= LLN
 - >=10 decrease and < LLN
 - >=20 decrease and >= LLN
 - >=20 decrease and < LLN

8.8.4. Immunogenicity Analyses

For each subject, the results and titers of anti-belantamab mafodotin binding antibodies and neutralizing antibody assay results will be listed for each assessment time point, along with ADC and total antibody concentration. The frequency and percentage of subjects with positive and negative anti-drug antibody and neutralizing antibody assay results will be summarized for each assessment time and overall for each subject by dose cohort.

The number and percentage of subjects with baseline anti-drug antibody results, overall and split by negative and positive samples in each treatment group will be provided. A further summary of subjects with post-baseline anti-drug antibody and neutralizing antibody results, anti-drug antibody negative (overall and for treatment-unaffected only), and treatment-emergent anti-drug antibody results (overall and split by treatment-induced and treatment-boosted) in each treatment group will be presented. Treatment-emergent anti-drug antibody is the sum of treatment-induced anti-drug antibody subjects and treatment-boosted anti-drug antibody positive subjects. Treatment unaffected anti-drug antibody is defined as a subject with an ADA-positive sample at baseline, in which post-baseline sample titer results are less than or equal to a four-fold increase in titer values relative to the baseline titer value (titer \leq 4x baseline titer) or was ADA negative anytime post baseline.

For treatment-induced and treatment-boosted subjects, a summary of all their titer values will be presented. Treatment-induced anti-drug antibody is defined as a subject with at least one post-baseline anti-drug antibody positive sample and an anti-drug antibody negative or missing baseline sample. Treatment-boosted anti-drug antibody is defined as a subject with an anti-drug antibody positive baseline sample in which at least one post-baseline sample titer value is four-fold greater than the baseline titer value (titer $>$ 4x

baseline titer) or if titer result is missing at baseline or missing at all post-baseline assessments.

8.8.5. Profile Plot

A profile plot for subjects will be produced. This plot will display the duration of study treatment in days for each subject, along with an indication of each subject's actual dose over time, investigator assessed confirmed response, highlighting responders versus non-responders, and those ongoing on belantamab mafodotin study treatment.

9. PHARMACOKINETIC ANALYSES

Concentration-time data collected in Cycle 1 will be analyzed using standard non-compartmental methods; some parameters will be determined for all participants and cycles, as data permit. The concentration-time data for belantamab mafodotin, total mAb, and/or cys-mcMMAF may be combined with data from other studies and analyzed in a population approach using nonlinear mixed effects modeling.

9.1. Drug Concentration Measures

Linear and semi-logarithmic individual concentration-time profiles will be plotted for belantamab mafodotin, total mAb, cys-mcMMAF, and pembrolizumab (if tested) in Part 1 and Part 2. Mean and median profiles (when applicable) will be plotted for each analyte by study part and belantamab dose cohort. Plasma concentrations of belantamab mafodotin, total mAb, cys-mcMMAF, and pembrolizumab (if tested) will be listed for each subject and summarized (when appropriate) by study part, belantamab mafodotin dose cohort, and planned time point. Refer to [Appendix 5: Data Display Standards & Handling Conventions](#) (Section 16.5.3 Reporting Standards for Pharmacokinetic)

9.2. Derived Pharmacokinetic Parameters

Concentration-time data for belantamab mafodotin, total mAb, cys-mcMMAF, and pembrolizumab (if measured) will be used.

The following pharmacokinetic parameters will be determined separately for each analyte, as data permit:

- Belantamab mafodotin and total mAb: Cmax, C-EOI, tmax, Ctrough, tlast, and AUC(0- τ)
- cys-mcMMAF: Cmax, C-EOI, tmax, tlast, and AUC(0-168)
- Pembrolizumab (if measured): Cmax, tmax, AUC(0- τ)

The pharmacokinetic parameters will be calculated by standard non-compartmental analysis according to current working practices and using Phoenix WinNonlin, version 6.3 or later, as data permit, or by population pharmacokinetic analysis (Section 10). Calculations of pharmacokinetic parameter values will be based on the actual sampling times recorded during the study.

The pharmacokinetic parameters C-EOI and Ctrough will be determined directly from the concentration-time dataset. Notes: For the dosing occasions with only predose and end of infusion samples, the end of infusion sample will not be identified as Cmax.

Table 7 Description of Pharmacokinetic Parameters

Parameter	Parameter Description
AUC(0-t)	Area under the concentration-time curve from time zero to the time of the last quantifiable concentration (C(t)) will be calculated using the linear trapezoidal rule for each incremental trapezoid and the log trapezoidal rule for each decremental trapezoid
AUC(0- τ)	Area under the concentration-time curve during the dosing interval
AUC(0-168)	Area under the concentration-time curve from time zero to 168 h after the start of the infusion
C-EOI	Concentration at the end of infusion
Cmax	Maximum observed concentration, determined directly from the concentration-time data for each cycle. Cmax will not be derived when only predose and EOI samples were collected.
tmax	Time to reach Cmax, determined directly from the concentration-time data for each cycle
Ctrough	Trough concentration prior to the next dose for each cycle
t $\frac{1}{2}$	Apparent terminal half-life will be calculated as: $t\frac{1}{2} = \ln(2) / \lambda_z$ (only from population PK analysis of belantamab mafodotin, if performed)
tlast	Time of last observed quantifiable concentration
CL	Clearance (only from population PK analysis of belantamab mafodotin, if performed)
Vss	Volume of distribution at steady state (only from population PK analysis of belantamab mafodotin, if performed)
λ_z , lambda_z	Terminal phase rate constant (only from population PK analysis of belantamab mafodotin, if performed)

NOTES:

- Only C-EOI and Ctrough may be derived when only predose and EOI samples were collected.
- Additional parameters may be included as required.

9.3. Summary Measure

Parameters listed in Section 9.2 will be summarized.

9.4. Population of Interest

The pharmacokinetic analyses will be based on the Pharmacokinetic population, unless otherwise specified.

9.5. Statistical Analyses / Methods

Unless otherwise specified, pharmacokinetic parameters defined in Section 9.2 will be listed and summarized descriptively (mean, standard deviation, median, minimum, maximum, geometric mean, and the standard deviation, CV% and 95% confidence interval of log-transformed parameters) by analyte, study part, and dose cohort and may be graphically presented, where appropriate. Summaries of pharmacokinetic parameter values from both Part 1 and Part 2 at the same belantamab mafodotin dose cohort may be generated.

Details of the planned displays are provided in Appendix 11: List of Data Displays and will be based on GSK Data Standards and statistical principles.

10. POPULATION PHARMACOKINETIC (POPPK) ANALYSES

Belantamab mafodotin, total mAb, and/or cys-mcMMAF concentration-time data may be analysed using a population pharmacokinetic approach. The planned population PK analysis will use the then-current population pharmacokinetic model(s) to generate *post hoc* pharmacokinetic parameter estimates (e.g., CL, V_{ss}, t_{1/2}, AUC(0- τ)) for the individual participants in this study on certain dosing occasions, data permitting. These parameter values will be listed and summarized as described in Section 9.5.

Based on the individual *post hoc* parameter values, dosing information, and sample collection times, drug concentrations at the time of sample collection will be predicted for each participant. Model evaluation will consist of comparison of model-predicted and observed concentrations. If necessary, model estimation will be performed.

Results of this analysis may be provided in a separate report.

To support this analysis, a population PK dataset will be generated. Detailed population PK methodology is also presented in [Appendix 9: Population Pharmacokinetic \(PopPK\) Analyses](#).

11. PHARMACOKINETIC / PHARMACODYNAMIC ANALYSES

If deemed appropriate and if data permit, exposure-response relationships between belantamab mafodotin exposure (e.g., concentration, Cmax, or AUC) and clinical activity and/or toxicity (e.g., response, AESIs) may be explored using population methods. If data permit, the effects of covariates may be explored.

If done, the analysis will be performed by, or under the direct auspices of, Clinical Pharmacology Modelling and Simulation (CPMS), GlaxoSmithKline, using the currently supported versions of all software packages. These analyses will be performed using R (The R Foundation for Statistical Computing), NONMEM (ICON Solutions) with PsN (Perl Speaks NONMEM), or another software platform deemed appropriate.

The results of this analysis may be provided in a separate report.

12. BIOMARKER ANALYSES

Description of exploratory biomarker data is intended for hypothesis generation in relation to the pharmacodynamics of belantamab mafodotin and/or combinations, for potential prognostic or predictive biomarker evaluation and/or for patient monitoring. Different shapes, colors, symbols and split plots will be used as appropriate to denote patient cohort, response group, dose group or other characteristics. On-treatment measurements may be visualized as percent or fold changes from baseline or as absolute values, as appropriate. Subjects may be plotted individually or in groups, as appropriate. Linear, semi-logarithmic, or logarithmic scales will be used for data visualization where appropriate. Linear interpolation will be used to visually connect measurements from individual subjects to aid interpretations, where appropriate.

If deemed appropriate and if data permit, relationships between biomarkers and/or pharmacodynamic markers and clinical activity and/or toxicity (e.g., response, AESIs) may be explored. If data permit, the effects of covariates may be explored. Details of these analyses will be reported either within the main clinical study report (CSR) or in a separate report.

Data measured from the following samples will be assessed in this RAP:

- Serum samples collected at pre- and post-belantamab mafodotin infusion and/or on-treatment to determine soluble BCMA (sBCMA) concentration by an electrochemiluminescent (ECL)-based MesoScale Discovery (MSD) immunoassays designed to detect GSK2857916 bound and free sBCMA.

12.1. Data processing

- Any out of range values defined by BISTRESC = BLQ or ALQ will be imputed respectively as LLOQ/3 or ULOQ and marked as out of range using distinct colors, shapes, or similar demarcation.
- Duplicate measurements for collections (same collection date/time) will be averaged across the duplicate measurements, when applicable.
- In cases where there are multiple pre-infusion collections (i.e. different collection date/time), the most recent measurement will be used as the baseline measurement.

12.2. Visualization and Tables

12.2.1. **Exploratory Objective: To evaluate PD markers in MM after treatment with belantamab mafodotin in combination with pembrolizumab.**

Endpoint: sBCMA concentration at baseline and on-treatment in subjects with MM and in relationship to clinical response.

12.2.1.1. Population of Interest

The biomarker/pharmacodynamic analyses will be based on the pharmacodynamic population in the All treated population, unless otherwise specified.

12.2.1.2. sBCMA

- Box plot showing absolute free sBCMA serum concentrations (log scale) measured at baseline in all participants, marked or separated by dose level and categorized by responders (participants with a best confirmed response (partial response (PR) or better)), non-responders (participants with best confirmed response (minimal response (MR), stable disease (SD) or progressive disease (PD))), and participants with best confirmed response of not evaluable (NE). Plots will illustrate the data gathered in Part 1 and Part 2 of this study.
- Spider plot showing absolute free sBCMA serum concentrations (log scale) measured at baseline and while on treatment versus the corresponding treatment cycle number or timepoint in all participants, marked or separated by dose level and categorized by responders (participants with a best confirmed response (partial response (PR) or better)), non-responders (participants with best confirmed response (minimal response (MR), stable disease (SD) or progressive disease (PD))), and participants with best confirmed response of not evaluable (NE). Plots will illustrate the data gathered in Part 1 and Part 2 of this study.
- Spider plot showing fold and/or percentage (%) change from baseline in free sBCMA serum concentrations (log scale) while on treatment versus the corresponding treatment cycle number or timepoint in all participants, marked or separated by dose level and categorized by responders (participants with a best confirmed response (partial response (PR) or better)), non-responders (participants with best confirmed response (minimal response (MR), stable disease (SD) or progressive disease (PD))), and participants with best confirmed response of not evaluable (NE). Plots will illustrate the data gathered in Part 1 and Part 2 of this study.
- Box plot showing absolute free sBCMA serum concentrations in relation to other disease burden markers, including but not limited to β 2 microglobulin, kappa/lambda free light chain, M-protein, etc. (log scale), measured at baseline in all participants, marked or separated by dose level and categorized by responders (participants with a best confirmed response (partial response (PR) or better)), non-responders (participants with best confirmed response (minimal response (MR), stable disease (SD) or progressive disease (PD))), and participants with best confirmed response of not evaluable (NE), and extramedullary disease. Plots will illustrate the data gathered in Part 1 and Part 2 of this study.

Table 8 below provides an overview of all the planned interim exploratory biomarker analyses in this RAP. Pre-defined assay parameters (e.g., dynamic range) will be used to identify and exclude from further analysis invalid biomarker data. Other biomarker variables may be examined in relation to other clinical variables, laboratory values, biomarkers, or safety endpoints, as deemed necessary.

Table 8 Overview of Planned Exploratory Analyses

[Endpoint /Parameter]	Untransformed or log-transformed											
	Absolute						% Change from Baseline					
	Statistical Analysis			Summary		Individual	Statistical Analysis			Summary		Individual
	T	F	L	T	F	F	L	T	F	L	T	F
sBCMA levels in subjects with MM												
Free sBCMA						Y						Y

NOTES :

- T = Table, F = Figure, L = Listing, Y = Yes display generated.
- Stats Analysis = Represents TFL related to any formal statistical analyses (i.e. modelling) conducted.
- Summary = Represents TF related to any summaries (descriptive statistics) of the observed raw data.
- Individual = Represents FL related to any displays of individual subject observed raw data.
- Either untransformed or log transformed analysis results will be presented, depending upon which is most appropriate for the data and analysis.

13. PATIENT REPORTED OUTCOMES ANALYSES

All questionnaires will be collected electronically as Electronic Patient Reported Outcomes (ePRO). The EORTC QLQ-C30 (version 3.0), EORTC QLQ-MY20, and the PRO-CTCAE are three oncology-specific Health-Related Quality-of-Life (HRQoL) assessments that will be analysed in this study.

In addition, the impact of potential corneal event on function and health-related quality-of-life will be assessed with the use of two visual function questionnaires, the NEI-VFQ-25 and Ocular Surface Disease Index (OSDI).

The analyses for EORTC QLQ-C30, EORTC QLQ-MY20, PRO-CTCAE, NEI-VFQ-25, and OSDI will be based on the All Treated population, unless otherwise specified.

13.1. Patient-Reported Outcome Version of the Common Term Criteria for Adverse Events (PRO-CTCAE)

The PRO-CTCAE is a patient-reported outcome measure developed to evaluate symptomatic toxicity in subjects on cancer clinical trials [Basch, 2014]. The PRO-CTCAE was designed to be used as a companion to the CTCAE, the standard lexicon for adverse event reporting in cancer trials. The PRO-CTCAE includes an item library of 124 items representing 78 symptomatic toxicities drawn from the CTCAE. PRO-CTCAE provides a systematic yet flexible tool for descriptive reporting of symptomatic treatment side effects in cancer clinical trials. In the present study, a subset of items selected from the PRO-CTCAE Version 1.0 Item library will be administered. The levels and related code values for PRO-CTCAE are shown below.

CCI - This section contained Clinical Outcome Assessment data collection questionnaires or indices, which are protected by third party copyright laws and therefore have been excluded.

CCI - This section contained Clinical Outcome Assessment data collection questionnaires or indices, which are protected by third party copyright laws and therefore have been excluded.

For each selected item from the library: proportion of PRO-CTCAE scores for attributes (frequency, severity and/or interference) will be presented with stacked bar charts by visit. Maximum PRO-CTCAE score at post-baseline for each item attribute will be summarized by counts and proportions. Proportion of patients with a maximum score of 3 or 4 for each item attribute (severe or very severe, frequently or almost constantly, quite a bit or very much) will also be reported. Proportions will be based on the number of patients with available data and subject with missing response will be excluded from analysis. A listing of the PRO-CTCAE score will be provided for each attribute (frequency, severity, interference, presence).

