• To characterize the relationship between clinical response and other biologic characteristics	• BCMA expression levels on malignant cells, serum sBCMA levels, serum cytokines, and immune cell characterization and their relationship to clinical response (Protein, RNA, DNA analysis).
• To investigate the relationship between genetic variants in the host and response to belantamab mafodotin in combination with pembrolizumab	• Possible relationship between host genetic variation and response to belantamab mafodotin administered in combination with pembrolizumab
• To explore the effect of belantamab mafodotin in combination with pembrolizumab on symptoms and health-related quality of life in subjects with RRMM	• Changes from baseline in symptoms and health-related quality of life as measured by the European Organisation for Research and Treatment of Cancer Quality of Life Questionnaire 30-item Core Module (EORTCQLQ-C30) and European Organisation for Research and Treatment of Cancer Quality of Life Questionnaire 20-item Multiple Myeloma Module (EORTC-QLQ-MY20)
• To evaluate the tolerability of belantamab mafodotin in combination with pembrolizumab based on patient self-report of symptomatic adverse effects	• Symptomatic adverse effects as measured by the PRO-CTCAE • Impact of ocular adverse effects on quality of life as measured by the Visual Function questionnaire(s): NEI-VFQ-25 and OSDI
• To evaluate disease and treatment related symptoms and associated impacts on function and health-related quality of life	• Exit Interview

¹ PK and ADA samples for pembrolizumab will be collected and stored during the trial. The analysis will be triggered if unexpected clinical findings have been identified.

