16.11.12. Health Outcomes Tables

Health Outcomes: Tables					
No.	Population	IDSL / Example Shell	Title	Programming Notes	Deliverable [Priority]
PRO-CTCAE					
6.001	All Treated	See programming notes	Summary of Maximum Post-Baseline PRO-CTCAE Score	Report for: Part 1, Part 2, and combined Part 1 and Part 2; Summarize by: dose level (Refer to Section 5.1 for ordering of dose level and omit 1.92 mg/kg if data is not available) Refer to mid205678 (primary_01) Table 8.0090 for guidance. For each selected item from PRO-CTCAE library: create summary Table for maximum post-baseline PRO-CTCAE score for each of 3 attributes (frequency, severity and/or interference). Presence/Absence will only be listed.	P-SAC [3], F-SAC [4]
OSDI					
6.002	All Treated	See programming notes	Summary of Change in OSDI Subscale Scores from Baseline	Report for: Part 1, Part 2, and combined Part 1 and Part 2; Summarize by: dose level (Refer to Section 5.1 for ordering of dose level and omit 1.92 mg/kg if data is not available) Refer to mid205678 (primary_01) Table 8.00130 for guidance; Additional	P-SAC [3], F-SAC [4]

Health Outcomes: Tables					
No.	Population	IDSL / Example Shell	Title	Programming Notes	Deliverable [Priority]
				timepoints includes EOT visit, last follow-up visit, and worst change from baseline.	
6.003	All Treated	See programming notes	Summary of Subjects with a 12.5 Point or Greater Deterioration from Baseline in the OSDI Vision-Related Function Subscale Score	
Report for: Part 1, Part 2, and combined Part 1 and Part 2; Summarize by: dose level (Refer to Section 5.1 for ordering of dose level and omit 1.92 mg/kg if data is not available); Refer to mid205678 (present_2020_04) Table 8.0160 for guidance. Include the following footnotes:
 
(1) Improvement is defined as a decrease from the worst subscale score of at least 12.5 points.
 
(2) Time to 12.5 point deterioration assessed only for those subjects experiencing a first worsening of at least one 12.5 unit as compared to the baseline score with complete onset date.
 
(3) Time to improvement is defined as time from the onset of first worsening of at least one 12.5 unit as compared to the baseline score to the first time of resolution based on 12.5 improvement from the first worst subscale score during the event.
	P-SAC [3], F-SAC [4]

Health Outcomes: Tables					
No.	Population	IDS / Example Shell	Title	Programming Notes	Deliverable [Priority]

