16.11.13. Health Outcomes Figures

Health Outcomes: Figures					
No.	Population	IDSL / Example Shell	Title	Programming Notes	Deliverable [Priority]
PRO-CTCAE					
6.001	All Treated	See programming notes	Stacked Bar Chart of PRO-CTCAE Score by Attributes and Visit	
Report for: Part 1, Part 2, and combined Part 1 and Part 2; Summarize by: dose level (Refer to Section 5.1 for ordering of dose level and omit 1.92 mg/kg if data is not available). Refer to mid205678 (primary_01) Figure 8.0010 for guidance. For each selected item from PRO-CTCAE library: create 5 sets of stacked bar charts per dose cohort for PRO-CTCAE score for each of 3 attributes (frequency, severity and/or interference).
	P-SAC [3], F-SAC [4]

Health Outcomes: Figures					
No.	Population	IDSL / Example Shell	Title	Programming Notes	Deliverable [Priority]
OSDI					
6.002	All Treated	See programming notes	Plot of Change from Baseline and Confidence Interval of OSDI Ocular Symptom Subscale Score by Visit	
Report for: Part 2 and combined Part 1 and Part 2; Summarize by: dose level (Refer to Section 5.1 for ordering of dose level and omit 1.92 mg/kg if data is not available). Refer to mid205678 (primary_07) Figure 8.10023 for guidance.
 
Add a dashed line at y axis=0.
 
In addition to treatment visits, also include end of treatment, worst case post treatment and last follow-up visits.
 
Add arrows showing direction of change from baseline: "deterioration" "improvement".
 
Add the following footnotes:
 
Note 1: Interval shown represents 95% confidence limits around mean at each planned time.
 
Note 2: "BSLN" represents "Baseline"; "EOT" represents "End of Treatment"; "WCPB" represents "Worst Case Post-baseline"; "LFU" represents "Last Follow-up".
	P-SAC [3], F-SAC [4]

Health Outcomes: Figures					
No.	Population	IDSL / Example Shell	Title	Programming Notes	Deliverable [Priority]

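### The PRO-CTCAE table reports only the raw post-baseline maximum, so it cannot separate symptoms present at baseline from those that worsened on treatment (minor; exploratory endpoint)

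*SAP*

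**What the plan says.** SAP Section 2.2 lists the endpoint as exploratory in both parts, under a tolerability objective. For Part 2 it reads "Symptomatic adverse effects as measured by the PRO-CTCAE".

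Section 13.1 plans four outputs:

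- Score proportions for each selected item, which "will be presented with stacked bar charts by visit".
- The tabulated summary: "Maximum PRO-CTCAE score at post-baseline for each item attribute will be summarized by counts and proportions".
- A threshold summary: "Proportion of patients with a maximum score of 3 or 4 for each item attribute".
- A listing of scores by attribute.

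The denominator rule is: "Proportions will be based on the number of patients with available data and subject with missing response will be excluded from analysis".

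In Section 16.11.12, Table 6.001 is the only PRO-CTCAE table. Its programming note says to "create summary Table for maximum post-baseline PRO-CTCAE score for each of 3 attributes", and it points to a table from another study for layout. In Section 16.11.13 the only PRO-CTCAE figure is Figure 6.001, "Stacked Bar Chart of PRO-CTCAE Score by Attributes and Visit". Listing 1.0061 (Section 16.11.15) gives item, visit, date, study day and the attribute scores.

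**The concern.** The summary is meant to describe tolerability. The trial has no control arm, and Section 2.3 requires at least three prior lines of therapy, so some subjects may enter with symptoms from disease or earlier treatment. The post-baseline maximum ignores where each subject started. A reader of Table 6.001 who sees a given percentage at 3 or 4 cannot tell how many of those subjects were already there before the first dose.

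What is at stake is interpretation: a patient-reported tolerability table that mixes baseline burden with on-treatment worsening, and gives no means of separating them within the table.

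**Working it through.** The SAP states no figure on this point, so there is none to reproduce. The check has two parts.

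**1. Is a baseline reference for PRO-CTCAE supplied anywhere?**

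| SAP place | Measure | Baseline used? |
|---|---|---|
| 13.2.1 NEI-VFQ-25 | Sub-scale scores by visit | Yes, change from baseline |
| 13.2.2 OSDI | Worsening of at least 12.5 points | Yes, from the baseline score |
| 13.3.1 QLQ-C30, 13.3.2 QLQ-MY20 | Domain scores | Yes, change from baseline |
| 8.7 Laboratory grades | Worst post-baseline grade | Yes, counted only if above the baseline grade |
| Table 3.0053 Punctate keratopathy | Eyes counted | Yes, only those worse than baseline |
| 13.1 and Table 6.001 PRO-CTCAE | Maximum post-baseline score | No |
| Figure 6.001 | Score proportions by visit | Not stated whether baseline is a bar; aggregate only |
| Listing 1.0061 | Individual scores by visit | Individual data; not a summary |

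PRO-CTCAE is the only questionnaire in the SAP whose summary has no baseline reference.

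**2. How large could the difference be?**

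Assumed inputs, none of them from the SAP:

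- p is the proportion scoring 3 or 4 on an item attribute at baseline.
- There is no treatment effect, so p is the same at every visit.
- There are K post-baseline assessments.
- Every subject has a baseline score, so both measures share one denominator.

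The raw measure counts a subject whose post-baseline maximum is 3 or 4. The adjusted measure used here also requires a baseline score below 3.

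*Bounds.* The difference consists of subjects who were at 3 or 4 at baseline and reach 3 or 4 again. It cannot be negative and cannot exceed p.

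*Full persistence (upper bound).* Raw = p, adjusted = 0, gap = p. For p = 10%, 20% and 30% the gap is 10, 20 and 30 points. With the roughly 28 subjects planned for Part 2 that is 2.8, 5.6 and 8.4 subjects.

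*Independent visits.* Raw = 1 − (1 − p)^K. Adjusted = (1 − p) × raw. Gap = p × raw. For K = 4:

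| p | Raw | Adjusted | Gap (points) |
|---|---|---|---|
| 10% | 1 − 0.9^4 = 34.4% | 0.9 × 34.4% = 31.0% | 3.4 |
| 20% | 1 − 0.8^4 = 59.0% | 0.8 × 59.0% = 47.2% | 11.8 |
| 30% | 1 − 0.7^4 = 76.0% | 0.7 × 76.0% = 53.2% | 22.8 |

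This calculation treats 3 and 4 as one category. The measure proposed under the fix would still count a subject who moves from 3 to 4, so its gap can only be equal to or smaller than the figures above.

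**The case against.** The strongest reply is that an accurately labelled descriptive summary is not wrong in itself. Several parts of that reply stand.

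- A reader might infer that the plan counts baseline symptoms as treatment side effects. The documents do not support that: no planned display labels the PRO-CTCAE scores as treatment-related or treatment-emergent. The suggestion comes only from the endpoint name and the tolerability objective. Attribution is handled elsewhere, through investigator-classified relatedness (Section 8.1, Table 3.0011) and the treatment-emergent flag (Section 16.4.2, Table 3.002). Baseline is therefore not the only way in this trial to separate disease from treatment.
- A reader might infer that Section 5.2 obliges the analysis to use baseline. It does not. It defines how a baseline value is derived and does not require every endpoint to be adjusted, so the two sections do not contradict each other.
- Figure 6.001 may already show the baseline distribution, if baseline counts as a visit, and the listing keeps individual scores. This is real context. It still does not tabulate how many subjects worsened.
- The layout that Table 6.001 follows is not shown, so a baseline column cannot be ruled out. The visible title and notes name only the post-baseline maximum.
- A baseline-adjusted score alone would hide persistent severe burden by setting it to 0. That would count against replacing the raw maximum, but not against adding a column beside it.

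**Conclusion.** The point holds in limited form. As specified, Table 6.001 cannot distinguish symptoms present at baseline from symptoms that worsened on treatment, and no other planned PRO-CTCAE display counts within-subject worsening.

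The size is unknown because the SAP gives neither baseline prevalence nor persistence. On the assumptions above, the overcount relative to a baseline-adjusted measure lies between zero and the baseline prevalence of scores 3 to 4. For an assumed 10% to 30% prevalence, the 10 to 30 points are a ceiling reached only if every burdened subject stays burdened. They should not be read as the expected excess. With four independent visits the figure is about 3 to 23 points.

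Adjustment also does not isolate a treatment effect. In the independent-visit case with no effect, the adjusted proportion is still 31.0% at p = 10%, because a maximum over several visits picks up fluctuation.

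The endpoint is exploratory and descriptive. No hypothesis, stopping rule or dose decision in the SAP rests on it. This is a minor improvement, not an error that affects a decision.

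**What to change.** Keep the raw maximum in Table 6.001 and make these additions:

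- For each item attribute, show the baseline score distribution.
- Add a baseline-adjusted maximum: the post-baseline maximum counted only if it is worse than the subject's own baseline score, and otherwise 0. Report the proportion with an adjusted score of 3 or 4.
- Show subjects without a baseline score as a separate row, and exclude them from the adjusted column.
- State in Section 13.1 and in the note to Figure 6.001 that baseline is displayed as a visit.

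The cost is one extra column per item attribute and a slightly smaller denominator for the adjusted column. No new data collection is needed where baseline scores exist, as the plan's use of a post-baseline maximum implies.
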